7.4.2 Data Storage

Investigators will extract the above data points from review of the EMR. It will then be entered into a REDCap password protected web-based database. **A REDCap data collection form (see attachment C) is attached.

All information gathered during this study will be kept confidential. At the time of subject providing study consent, a unique numerical identifier (sequential in study) will be assigned to the subject in lieu of personal identifying information and this numerical identifier will be used to code all clinical data abstracted from the medical record. A key linking the patient name, date of birth, and medical record number to this study identifier will be created and maintained by the study principal investigator that will not be shared with non-study members. The key will be maintained on an encrypted, firewalled, and password protected computer file.

7.5 ASSESSMENT/EVALUATION PLAN

The primary outcome of this study will be to assess the feasibility of a future multicenter, randomized controlled trial. Outcomes that will be analyzed include:

- Rate of enrollment: # of patients enrolled / # of patients screened
- Drop-out rate for randomization: # of patients who do not finish treatment as assigned / # of patients randomized
- Rate of patients who require escalation of care: # of patients requiring completion lobectomy / # of patients in the thyroid lobectomy randomization arm

Secondary endpoints will be whether molecular-risk category predicts American Thyroid Association risk category⁵ that incorporates histopathological findings, percentage of patients requiring thyroid hormone supplementation or replacement, short-term quality of life. Our study is designed as a feasibility study, and is under-powered to assess oncologic outcomes.

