To date, no randomized control trial exists comparing extent of surgery based on preoperative molecular data. We envision a future clinical trial where thyroid cancer patients undergo risk stratification with molecular testing, and subsequently intermediate-molecular risk patients get randomized to thyroid lobectomy versus total thyroidectomy. To determine how to adequately power this endeavor, we propose a pilot randomized clinical trial as an initial feasibility study. We hypothesize that 1) patients with papillary thyroid cancer will agree to preoperative molecular testing, and 2) 50% of intermediate molecular-risk patients will agree to randomization to thyroid lobectomy versus total thyroidectomy and complete treatment as assigned.

Patients referred to our Endocrine Surgery Clinic with new diagnosis of papillary thyroid cancer (Bethesda V or VI on cytology) will be enrolled and undergo routine molecular testing. We will exclude patients with hard indications for total thyroidectomy on ultrasound imaging (nodal or distant metastases, extrathyroidal extension). Patients' thyroid cancer molecular profile will be classified as low, intermediate, or high molecular-risk based on previous published data. There is equipoise between thyroid lobectomy and total thyroidectomy for intermediate risk molecular profile thyroid cancers. Thus, we will randomize those patients to thyroid lobectomy or total thyroidectomy. Endpoints are related to feasibility of a future trial. We will assess percentage of patients who 1) agree to randomization, and 2) complete treatment as assigned.

We will simultaneously create a registry tracking the final surgical pathology and clinical results of low and high molecular-risk patients. Postoperative pathologic findings following thyroid surgery will be obtained using chart review. We will determine whether certain mutations and molecular risk profiles predict the need for RAI treatment. Additionally, we will track postoperative cancer surveillance outcomes, including biochemical and structural evidence of recurrence.

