Molecular analysis and associated with aggressive disease. Commercially available molecular testing was first developed to discriminate benign from malignant thyroid nodules when cytology was indeterminate. Over time, there has been a growing understanding that certain molecular profiles are associated with worse clinical outcomes. Yip et al. verified a method of risk stratification of thyroid cancers based on their molecular profile by performing a propensity-matched retrospective molecular analysis of 62 differentiated thyroid cancers with distant metastases to those without distant metastases.¹¹ They found that high-

molecular risk profiling had a strong association with distant metastases (odds ratio 25.1, 95% confidence interval [CI] 3.07 – 204.4) and no patients with low-molecular risk had metastatic disease. In this instance, molecular profile predicted clinical behavior, which led us to hypothesize that molecular risk could be used to dictate therapy in thyroid cancer. This molecular risk stratification is utilized by Thyroseq (Figure 1).

Most recently, our group published a retrospective study of molecular profiles of 100 Bethesda V and VI thyroid nodules and assessed their associated risk of recurrence. Majority of the nodules in this population harbored an intermediate molecular-risk profile (6 low-risk, 88 intermediate-risk, and 6 high-risk). ¹² Similar to the study by Yip et al., high-molecular risk patients had higher rates of recurrence at 67% compared to intermediate-risk at 7%, and no recurrence in the low-risk cohort. High-risk molecular profile was associated with risk of disease recurrence in the 5-year follow-up period (hazard ratio 1.36, 95% CI 1.02 – 1.80). Based upon this data, it appears that total thyroidectomy can be reserved for high-risk individuals and thyroid lobectomy in low-risk patients. However, the ideal extent of initial surgery in intermediate-risk disease remains unclear.

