5. STUDY OBJECTIVE

[figure not shown]
Aim 1. Determine feasibility of a future multi-center prospective trial of routine preoperative molecular testing for papillary thyroid cancers to guide extent of therapy. Patients with a new diagnosis of papillary thyroid cancer will undergo routine molecular testing with Thyroseq genomic classifier. Inclusion criteria include age over 18 years and cytology consistent with papillary thyroid cancer. We will exclude patients with hard indications for total thyroidectomy on ultrasound imaging (nodal or distant metastases, extrathyroidal extension). Patients' thyroid cancer molecular profile will be classified as low-, intermediate-, or high-risk based on previous published data. 11,12 Endpoints are related to feasibility of a future trial, including enrollment rate among eligible patients and drop-out rate among enrolled patients.

Aim 2. Determine the percent of eligible patients that undergo randomization to thyroid lobectomy versus total thyroidectomy and complete assigned treatment. There is equipoise between thyroid lobectomy and total thyroidectomy for intermediate risk molecular profile thyroid cancers. Thus, we will randomize those patients to thyroid lobectomy or total thyroidectomy. However, many patients may object to randomization or may not be willing to undergo treatment as randomized. Thus, we will assess percentage of patients who 1) agree to randomization, and 2) complete treatment as assigned.

Aim 3. Determine whether preoperative molecular testing predicts postoperative clinicopathologic findings by creating a registry tracking the final surgical pathology and clinical results.

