7.2.5 Target Enrollment

For feasibility studies of randomized control trials, a sample size of 24 to 50 patients is recommended. We hypothesize that 50% of intermediate-risk patients will agree to and complete the treatment as assigned. Therefore, in order to end with a total of 50 patients in the randomization cohort, we will need 100 patients with intermediate-risk disease. The UCLA Endocrine Center is a high-volume tertiary referral center, performing 300 thyroid operations annually. Of these patients, approximately 200 patients per year have localized disease eligible for this study. Based on our clinical volume, this is achievable in a one-year enrollment period.

- Total goal enrollment N = 100
- Total goal enrollment of intermediate molecular risk patients into randomization cohort N = 50

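### Section 7.5 puts enrolment on a different denominator from Aim 1, can count patients before consent, and leaves out the agree-and-complete proportion on which the sample size rests

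*Combined protocol and SAP*

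**What the plan says.** **Promised.** Hypothesis 2 in the abstract (section 2) is that "50% of intermediate molecular-risk patients will agree to randomization to thyroid lobectomy versus total thyroidectomy and complete treatment as assigned". The abstract adds: "We will assess percentage of patients who 1) agree to randomization, and 2) complete treatment as assigned". In section 5, Aim 2 is to "Determine the percent of eligible patients that undergo randomization to thyroid lobectomy versus total thyroidectomy and complete assigned treatment", and Aim 1 names as endpoints the "enrollment rate among eligible patients and drop-out rate among enrolled patients".

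**Sized on.** Section 7.2.5 states "We hypothesize that 50% of intermediate-risk patients will agree to and complete the treatment as assigned" and concludes that "we will need 100 patients with intermediate-risk disease" to finish with 50 in the randomised cohort.

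**Listed for analysis.** Section 7.5 gives three ratios under the primary feasibility outcome. The first is "Rate of enrollment: # of patients enrolled / # of patients screened". The second is a drop-out rate for randomisation: those not finishing as assigned, over those randomised. The third is the rate of further surgery in the lobectomy arm. The list is introduced with the word *include*.

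**Who counts as enrolled.** Section 7.2.3 has patients enrolled while molecular results are pending, or while they take more time to decide, with consent to follow. The telehealth route works the same way. Patients who prove ineligible are withdrawn from enrolment. Section 7.4.2 assigns the study identifier at consent, but does not say that this is what enrolled means in section 7.5.

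**The concern.** The pilot exists to tell the planners of a multicentre trial how many eligible patients will consent, accept randomisation and then have the operation assigned. The analysis section should define each of those quantities, and it falls short in three ways.

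- The enrolment denominator in section 7.5 is not the one in Aim 1.
- The enrolment numerator can include people who have only expressed interest. Someone who is enrolled before consent and then refuses is exactly the refusal that a feasibility study needs to count.
- Neither agreement to randomisation nor the joint agree-and-complete proportion has a listed numerator and denominator, although the 50% hypothesis and the sample size both refer to the joint proportion.

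If the definitions stay open, they will be chosen after the counts are known, and the future trial may be planned on a rate that is not acceptance among eligible patients.

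**Working it through.** **1. The plan's own figure.** Section 7.2.5: target 50, hypothesised agree-and-complete rate 0.50. Number needed = 50 / 0.50 = 100. This reproduces the stated 100, so the size rests on the joint proportion.

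**2. Does section 7.5 determine that proportion?** Let N be the intermediate-risk patients, R those randomised and d the section 7.5 drop-out rate. Then joint proportion = R(1 − d)/N. Section 7.5 supplies d but no R/N.

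With N = 100 and d = 10% (assumed):

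| Randomised | Joint proportion |
|---|---|
| 30 | 30 × 0.9 / 100 = 27% |
| 50 | 50 × 0.9 / 100 = 45% |
| 70 | 70 × 0.9 / 100 = 63% |
| 90 | 90 × 0.9 / 100 = 81% |

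Conversely, a joint proportion of exactly 50% requires d = 1 − 0.50/agreement. That is 0% at 50% agreement, 33.3% at 75% and 50% at 100%. The drop-out rate by itself therefore cannot show whether hypothesis 2 was met.

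**3. Precision once the proportion is defined.** For 50 of 100, the exact (Clopper-Pearson) 95% interval is 39.8% to 60.2%.

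**4. The enrolment rate.** Let C be patients who sign consent, D those enrolled before consent who later decline, S those screened and L those eligible.

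- Section 7.5 as written allows (C + D)/S.
- Aim 1, with enrolment counted at consent, gives C/L.
- The ratio of the first to the second is (1 + D/C) × (L/S).

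The first factor is at least 1. The second is at most 1, because section 7.2.3 describes screening as starting from the medical record, before interview, ultrasound and molecular results settle eligibility. The two faults push in opposite directions. The documents give none of C, D, S or L as study counts, so neither the size nor the sign of the net distortion can be determined.

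**5. Drop-out.** Aim 1 sets drop-out against enrolled patients. Section 7.5 sets non-completion against randomised patients and labels it as concerning randomisation. These are two measures that can coexist, but section 7.5 lists only the second.

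**The case against.** The best defence is that nothing essential is lost. The abstract and Aim 2 commit to reporting agreement and completion, the section 7.5 list is not worded as exhaustive, and its ratios are built from counts. With 100 intermediate-risk patients, the joint proportion is simply (randomised − not finishing)/100. That largely stands. The 27% to 81% spread applies only if rates are reported without counts, and a reader who inferred that hypothesis 2 has no planned assessment would go too far.

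Two other strong readings are tempting.

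- Hypothesis 2 speaks of intermediate-risk patients and Aim 2 of eligible patients. One might therefore infer that the completers could be divided by the roughly 200 localised cases a year in section 7.2.5, so that a pilot exactly on target appears to miss its 50%. The documents do not support this. Section 7.2.1 makes an intermediate-risk result an inclusion criterion, the text of Aim 2 says that these are the patients to be randomised, and the 200 is a yearly volume offered to show that accrual is achievable.
- One might read the two drop-out definitions as a contradiction. As shown above, they can stand together; the gap is that one of them is not listed.

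On pre-consent enrolment, the consent-linked identifier in section 7.4.2 gives a ready count of consented patients. That helps, but no text ties it to the section 7.5 numerator.

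The statements here about what is absent rest on the text. The schema graphic and the data collection form were not available.

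**Conclusion.** The concern holds as a defect of definition in the primary feasibility outcomes, and should be fixed before the rates are reported.

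- **Enrolment rate.** The denominator contradicts Aim 1, and the numerator as written can include patients who never consent. Followed literally, it does not measure consented acceptance among eligible patients. The amount of distortion cannot be determined.
- **Agreement and agree-and-complete.** Both are missing from the section 7.5 list although promised elsewhere and, for the joint proportion, used for sizing. This is an omission from a list, not an unplanned outcome.
- **Aim 1 drop-out.** It is not listed in section 7.5.

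The figure of 100 is not in dispute. The 10% drop-out used in the illustration is an assumption.

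**What to change.** 1. In section 7.5, add two primary feasibility outcomes on one denominator: eligible intermediate-risk patients (section 7.2.1 criteria) who are offered randomisation. The numerators are those randomised, and those randomised who complete as assigned. Report exact 95% intervals, and state that the 50% hypothesis refers to the second.
2. Make enrolled/eligible the enrolment rate, as in Aim 1, with enrolled/screened as a supplementary figure.
3. In section 7.2.3, count a patient as enrolled only at signed consent, in line with the identifier rule in section 7.4.2. Log the eligible patients approached and those who decline.
4. State whether the 100 in section 7.2.5 means patients approached or patients consented, since the text does not settle this. Align section 9.2 with the answer, because its safety review is triggered by each 10 subjects enrolled. For example, if 100 were approached and half consented (assumed), the trigger would be reached 50/10 = 5 times, not 100/10 = 10.
5. Give the two drop-out measures separate names and list both.

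The cost is protocol wording and a short screening log, with no extra patients or procedures. The reported enrolment count may look less favourable than one that includes interest before consent.

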7.3.7 Indications for Postoperative RAI and Completion Thyroidectomy

Indications Postoperative RAI

Patients who ultimately result with aggressive disease on histopathology will need postoperative RAI to reduce the risk of disease recurrence, which is in accordance with the 2015 ATA Guidelines. Indications include:

- Gross extrathyroidal extension of the cancer seen at time of operation
- Lymph node metastasis, which is defined as
 - o 1 or more lymph node with a > 2mm metastasis
 - o 5 or more lymph nodes with a \leq 2mm metastasis
 - o Extranodal extension of metastasis

- Aggressive histology (diffuse sclerosing, insular, Hurthle cell, solid, hobnail, columnar cell variant, and high-grade follicular cancer)
- Multifocal vascular invasion
- Microscopic margin positivity

Completion Thyroidectomy

Patients who initially underwent thyroid lobectomy and pathology ultimately return with the indications listed above for postoperative RAI need to undergo completion thyroidectomy. All patients who undergo thyroid lobectomy have their pathology sent for rush pathology, which will result 48 hours later. If patients need a completion thyroidectomy, the surgeon will call them with this information and book a second operation. The surgical team will perform informed consent for the operation on the day of the surgery and patients will receive the usual peri-operative care as listed above.

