7.4 DATA MANAGEMENT

7.4.1 Data Collection

Patient's data will be collected via review of the patient's electronic medical record (EMR), which will be reviewed weekly. Data points to be recorded include:

- Patient demographics: age, sex, BMI, date of birth
- Comorbid endocrine disease: concurrent hypo/hyperthyroid disease, parathyroid disease, neuroendocrine tumor
- Prior or current cancer diagnosis
- Medications
- Bethesda category of FNA
- ThyroSeq results (specific mutation(s) present, cancer risk classifier results)
- Type of operation (thyroid lobectomy, total thyroidectomy, completion thyroidectomy)
- Ultrasound imaging results
- Laboratory values (Tg, Tg antibody, TSH, Calcium, PTH)
- Pathology results
- RAI dosing
- Thyroid hormone medication dosing
- Presence of postoperative complications: neck hematoma, reoperation, hypocalcemia, recurrent laryngeal nerve injury, voice hoarseness, readmission, reason for readmission

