9.3 Planned stopping rules for the study

The study will be stopped entirely or for a specific subgroup if there is greater than 50% incidence of serious adverse events due to study procedures, such as infection, as well as greater than 50% of thyroid lobectomy patients requiring completion thyroidectomies and early cancer recurrence in the low and intermediate risk group. The rate of completion thyroidectomies will be reviewed and calculated every 10 participants who were randomized to thyroid lobectomy.

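### Does the escalation rate need a second denominator, lobectomies performed, beside patients randomized to lobectomy?

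*Combined protocol and SAP*

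**What the plan says.** Section 7.5 lists three feasibility outcomes. Two matter here. Escalation of care is the number "of patients requiring completion lobectomy / # of patients in the thyroid lobectomy randomization arm". Drop-out is the number "of patients who do not finish treatment as assigned / # of patients randomized", with no split by arm.

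Section 7.3.7 says who can need the second operation: "Patients who initially underwent thyroid lobectomy and pathology ultimately return with the indications listed above for postoperative RAI need to undergo completion thyroidectomy". Aim 2 in section 5 expects imperfect adherence, since "many patients may object to randomization or may not be willing to undergo treatment as randomized". Section 7.2.5 bases the target on the hypothesis that "50% of intermediate-risk patients will agree to and complete the treatment as assigned".

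Section 9.3 includes a threshold of "greater than 50% of thyroid lobectomy patients requiring completion thyroidectomies" and has that rate "reviewed and calculated every 10 participants who were randomized to thyroid lobectomy". Section 7.4.1 lists among the data points "Type of operation (thyroid lobectomy, total thyroidectomy, completion thyroidectomy".

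**The concern.** Only a patient who had a lobectomy can need completion, yet the denominator is everyone allocated to lobectomy. If some of that arm refuse or switch, the escalation rate mixes two quantities: how often a lobectomy leads to a second operation, and how often the assigned lobectomy takes place. Because drop-out is pooled, a reader of the two rates cannot separate them. The pilot is meant to inform a multicenter trial in which adherence may differ, so planners would want each part.

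The same question reaches section 9.3, whose threshold does not say whether lobectomy patients are counted as randomized or as operated. Near 50% the choice could decide whether the threshold is passed. Section 7.5 also speaks of completion lobectomy where sections 7.3.7, 7.4.1 and 9.3 speak of completion thyroidectomy.

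**Working it through.** **Inputs from the documents.** 50 patients in the randomization cohort (section 7.2.5) and 1:1 allocation (section 7.3.5), so about 25 per arm. The plan's own sample-size step reproduces: 50 / 0.5 = 100 intermediate-risk patients. The documents state no escalation rate and no rate of non-receipt after randomization; all such values below are assumptions.

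**Relation between the two rates.** Let N be the number randomized to lobectomy, m the number of these who had it, and x the number needing completion. Then x/N = (x/m)(m/N) = p(1 − d), where p is the rate per lobectomy and d the share of the arm that did not have one. For p = 40%:

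- d = 10%: 0.40 × 0.9 = 36%
- d = 20%: 0.40 × 0.8 = 32%
- d = 30%: 0.40 × 0.7 = 28%

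**What the two planned summaries leave open.** Assume 8 completions among 25 and 5 drop-outs among 50, all of them patients who did not have the assigned operation. If k of the 5 were in the lobectomy arm, p = 8/(25 − k):

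| k | 0 | 1 | 2 | 3 | 4 | 5 |
|---|---|---|---|---|---|---|
| p | 32.0% | 33.3% | 34.8% | 36.4% | 38.1% | 40.0% |

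The exact (Clopper-Pearson) 95% interval is 14.9% to 53.5% for 8/25 and 19.1% to 63.9% for 8/20. The largest shift, 8 percentage points, is small beside either interval.

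**What the data leave open.** Section 7.4.1 records lobectomy and completion thyroidectomy for each patient. The allocated arm is not named in that list, but section 7.5 cannot be computed without it. With both in hand, m and x are counts, and p = x/m needs no inference from pooled drop-out.

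**Section 9.3.** Take 10 randomized and assume 9 had the operation. Above 50% as randomized needs x ≥ 6; above 50% as operated needs x ≥ 5. The readings differ only at x = 5 (5/10 = 50.0%, 5/9 = 55.6%). With X ~ Binomial(9, p), P(X = 5) is 1.7%, 7.4%, 16.7% and 24.6% at p = 20%, 30%, 40% and 50%. With 20 randomized and 18 operated they differ only at x = 10 (10/20 = 50.0%, 10/18 = 55.6%), with probability 0.1%, 1.5%, 7.7% and 16.7%. If all 10 have the assigned operation, the readings are identical.

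**Which reading the text supports.** Section 7.5 uses the allocated arm as denominator for the same rate. Section 9.3 ties both the review and the calculation of the rate to participants randomized to lobectomy. Section 8.1 describes the reoperation risk for patients randomized to lobectomy. All three point the same way.

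**Completion lobectomy.** Section 7.3.6 describes completion thyroidectomy as removal of the remaining lobe, so both terms mean the same operation.

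**The case for a change.** The best case for a change is that non-adherence is one of the things this pilot sets out to measure, so it should not be assumed away. Larger drop-out widens the gap. With an assumed 10 drop-outs among 50, the lobectomy arm could have between 15 and 25 operations, and 8 completions would mean anything from 8/25 = 32% to 8/15 = 53.3% per lobectomy. In section 9.3, with 8 of 10 operated and p = 50%, the chance of passing the threshold at the first review is 0.145 as randomized and 0.363 as operated. Refusal may also differ between the arms, which a pooled rate would hide. The extra reporting would cost only a line or two.

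The arithmetic stands, and showing completions per lobectomy and non-receipt by arm would be a helpful line in the report. It does not show that the planned rate is wrong. The per-lobectomy group is selected after randomization, so it could only supplement the planned rate, and if everyone has the assigned operation it adds nothing. The range to 53.3% also requires all 10 drop-outs to fall in one arm and all to be non-receipt; a patient who had the lobectomy and left later may count as a drop-out too. For that reason drop-out by arm would not by itself give the number of lobectomies. The operation record does.

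On section 9.3, it remains true that the denominator is never stated outright. The surrounding text leaves a sensible default.

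**Conclusion.** No change to the plan is needed. The escalation rate in section 7.5 has an explicit denominator and answers a legitimate question: of patients allocated to lobectomy, how many go on to a second operation. The complementary rate per lobectomy is missing from the listed outputs but not from the data, and an analyst can tabulate it directly.

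In the assumed case with 10% pooled drop-out, the two rates differ by at most 8 percentage points (32.0% against 40.0%), well inside the sampling error of about 25 patients per arm. The difference vanishes if all patients have the assigned surgery. Section 7.2.5 can be read as counting 50 patients who complete as assigned, which would put non-receipt near zero.

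The unstated denominator in section 9.3 is a detail that section 7.5 and the next sentence of 9.3 fill. In the cases worked with 8 or 9 of 10, or 18 of 20, operated as assigned, it matters at one count per review. The completion lobectomy wording is clerical. The conclusion assumes that allocated arm and operation performed are both held for each patient, as section 7.5 and section 7.4.1 imply; the data collection form itself is not in the text.
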